5.2 Surgical resection of all detectable melanoma

5.2.1 Treatment Group A

Subjects in Group A will have complete surgical resection of all detectable melanoma following Course 1 of hu14.18-IL2. Surgical resection will be scheduled for 7-14 days following the completion of the first 3-day course of therapy (i.e., days 10-17) in order to insure reversal of hu14.18-IL2 toxicities prior to the surgery. These ranges will allow enough flexibility so that the appropriate surgical subspecialist will be available to perform the resection.

Once the subject has recovered from the surgery (2-4 weeks, depending upon the nature of surgery (Section 4.4.8), the subject will begin Course 2 of treatment. Decisions regarding whether a subject has recovered sufficiently from surgery to begin Course 2 of treatment will be left to the discretion of the treating physician(s). To aid in this decision, laboratory tests may be ordered as warranted clinically, but no specific tests are required for this assessment. Subjects undergoing “extensive surgery” (see Section 4.4.8) will not begin Course 2 of study treatment until at least 21 days after surgery. Subjects undergoing “non-extensive surgery” will not begin Course 2 of study treatment until at least 14 days after surgery (see Section 4.4.8). No course of hu14.18-IL2 therapy will be administered sooner than 4 weeks after day 1 of the prior course of hu14.18-IL2 therapy. Subjects will receive a total of 3 courses of treatment as described in Section 5.3.

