5.2.2 Treatment Group B

Subjects in Group B will have complete surgical resection of all detectable melanoma upon study entry, prior to Course 1 of hu14.18-IL2. Once the subject has recovered from the surgery (2-4 weeks, depending upon the nature of surgery (Section 4.4.8), the subject will begin Course 1 of treatment. Decisions regarding whether a subject has recovered sufficiently from surgery to begin Course 1 of treatment will be left to the discretion of the treating physician(s). To aid in this decision, laboratory tests may be ordered as warranted clinically, but no specific tests are required for this assessment. Subjects undergoing “extensive surgery” (see Section 4.4.8) will not begin Course 1 of study treatment until at least 21 days after surgery. Subjects undergoing “non-extensive surgery” will not begin Course 1 of study treatment until at least 14 days after surgery (see Section 4.4.8). No course of hu14.18-IL2 therapy will be administered sooner than 4 weeks after day 1 of the prior course of hu14.18-IL2 therapy. Subjects will receive a total of 3 courses of treatment as described in Section 5.3.

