will not be considered as disease progression, and the subject can continue on study, provided the identifiable melanoma is completely resectable, and the subject has not had irreversible DLT from the protocol therapy that delays the surgery to 8 weeks after administration of cycle 1 protocol therapy.

⁶ Tumor assessment will only be done if toxicity from the surgery is so prolonged that it delays starting the second course of study therapy by 4 or more weeks from the anticipated time (post-op day 14 for non-extensive surgery or post-op day 21 for extensive surgery). If initiation of course 2 therapy is delayed by ≥ 4 weeks, radiographic assessment of tumor status is required within 2 weeks of starting Course 2 of study therapy.

TABLE 6B.

CLINICAL ASSESSMENT GUIDELINES FOR THE SURGICAL RESECTION AND POST-OP PERIOD: GROUP B (SURGERY BEFORE COURSE 1 OF STUDY THERAPY)

	Pre-Operative¹	Immediate Post-operative²	≤ 1 week before starting hu14.18-IL2³
Physical Exam		X	X
Weight	X	X	X
Performance Status	X		X
Tumor Assessment			X⁴
Vital signs (T, BP, P, RR)	X	X	X
CBC, diff, plts			X
AST, ALT, T bili, alk phos, alb, LDH, Na, K, Cl, HCO ₃ , Cr, BUN, Glucose, Ca, Mg, Phosphate			X
INR/PTT			X
Urinalysis			X

¹ The pre-operative studies indicated here can be done the day of or the day before surgery

² Post-operative management and tests required should be those felt to be needed for patient care by the surgical team.

³ The exact tests to be ordered will be left to the discretion of the treating physician(s) as they are warranted clinically to assess recovery from surgery. It is anticipated that these tests will be obtained 1-3 weeks post-operatively, depending on the nature and extent of the surgery, and the post-operative recovery. If the results of these tests suggest the subject has not fully recovered from surgery, additional clinical evaluation may be required to identify the cause of the abnormality and to provide treatment if indicated. Tests may be repeated as needed until adequate resolution so the patient may begin Course 1 of hu14.18-IL2, preferably within 4 weeks of surgery. If 8 weeks pass post-operatively, and the treating physician(s) still feel(s) that the subject is not fit to continue, the subject will not receive hu14.18-IL2.

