7.4.2 Anti-hu14.18-IL2 antibody levels

Serum specimens will be obtained at the indicated times shown in Table 7A and cryopreserved. These will then be tested in ELISA assays currently in use (36) and now being developed to detect and quantitate antibody against the hu14.18-IL2 IC molecule.

TABLE 7A.
IMMUNOLOGICAL AND PHARMACOKINETIC ASSESSMENT

	Base Line ¹	Week 1				Week 2	Week 5
DAY		1 ²	2	3	4	8	29(1) ^{2,3}
Hu14.18-IL2		X	X	X			
Serum hu14.18-IL2 levels ⁴		X/X	X/X	X/X			
Soluble IL2 receptor	X	X/C1		X/C1	X	X	X
Anti- hu14.18-IL2 Ab	X	X/C1		X/C1	X	X	X
Red top tubes (mL) ⁴	2x10	2x10/1x10; 3x10	1x10/1x10	2x10/1x10	1x10	1x10¹¹	1x10¹⁰
In vitro NK/ADCC studies ⁵	X					X C2+3	X C2+3
Green top tubes (mL) ⁵	1x10					1x10 C2+3	1x10 C2+3
In vitro T cell studies ^{6,7}	X^{6,7}						X^{6,7} C2+3
Heparinized syringe (mL) ^{6,7}	50						50^{6,7} C2+3
In vivo binding ⁸	X				X		

X/ = pre-IC⁹

/X = post-IC⁹

¹ Studies scheduled for “Baseline” can be obtained at any time from 3weeks prior to randomization until just prior to (within 10 minutes) beginning study treatment.

² Day 29 of each course (+/- 7 days leeway to facilitate clinical scheduling) = day 1 of subsequent course.

³ These tests may be performed up to 1 week prior to initiating the next course of therapy (day 22-29 of current course).

⁴ To better understand the pharmacokinetics of hu14.18-IL2 serum will be obtained from subjects in both groups for all courses to measure hu14.18-IL2 levels at the following times: pre and post the 4 hr IC infusion and again 2, 4, and 8 hours after completion of the 4-hr IC infusion on days 1 and 3; on day 2, only the pre- and post-IC samples will be collected.

- ⁵ *In vitro* testing of NK and ADCC function will be performed on selected patients five times with 10 mL of heparinized blood: at baseline, on day 8 of Courses 2 and 3 (C2+3) and within one week of the end of Courses 2 and 3. Additional lymphocytes obtained at the day 8 time points will be cryopreserved for subsequent DNA analyses.
- ⁶ Lymphocytes will be cryopreserved for subsequent T cell function testing from 50 mL of heparinized blood. Plasma collected with this sample also will be cryopreserved for subsequent immunological assays. This sample will be obtained three times: once at baseline, and within one week of the end of both Courses 2 and 3 (C2+3).

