9.4.2 Baseline Comparability

All measurements (variables) collected at baseline will be summarized and compared between study arms. If the pre-treatment value is missing, the measurement recorded at the screening visit will be substituted. Significant unbalances found between study arms may be considered as covariates in exploratory analyses of primary endpoints (i.e., pathology evaluations of necrosis, apoptosis, and cellular infiltrate).

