9.4.5 Secondary Endpoints

The number and severity of toxicity incidents will be analyzed descriptively in tabular format. Immunological parameters, i.e., lymphocyte counts, NK/ADCC, soluble IL2, anti-idiotypic antibodies, and anti Fc-IL2, will be summarized by standard descriptive statistics in terms of means, standard deviations, medians and ranges for each measurement time point (see Section 7.3) and group separately. Within each group, differences between pre-IC treatment values and post-IC treatment values will be evaluated by paired t-tests and/or non-parametric Wilcoxon test.

Comparisons of immunological parameters between the two study arms will be performed by two-sample t-tests. Furthermore, longitudinal data analyses of immunological parameters will be performed to incorporate the time effect. Specifically, linear and/or nonlinear mixed effect models with subject specific random effects and generalized estimating equations (GEE) models with identity link and exchangeable (working) correlation structures will be used to account for the correlation between repeated measurements of immunological parameters. Missing data may be imputed using regression type imputation techniques. For immunological parameters not conforming to the assumptions of parametric analysis, the non-parametric Wilcoxon Rank Sum test will be used for comparing the two study arms. The association between the various immunological parameters will be examined by computing Spearman's rank correlation coefficients and linear or nonlinear regression techniques. Immunological parameters will be correlated with clinical endpoints by fitting Cox regression models (for clinical endpoints overall survival & time to recurrence) and logistic regression analysis models (for clinical endpoints toxicity and histological evidence of anti-tumor activity). The data of all immunological parameters will be presented graphically where possible (boxplots, histograms, profile plots and scatterplots).

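### In the surgery-first arm, the single NK/ADCC and T-cell baseline may be drawn before or after the operation, so the within-arm pre/post change can mix surgery with the drug

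*Combined protocol and SAP*

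**What the plan says.** Section 5.2.2 states: "Subjects in Group B will have complete surgical resection of all detectable melanoma upon study entry, prior to Course 1 of hu14.18-IL2". Course 1 follows recovery ("Once the subject has recovered from the surgery (2-4 weeks, depending upon the nature of surgery"), and after extensive surgery subjects "will not begin Course 1 of study treatment until at least 21 days after surgery". Study treatment in this protocol therefore means the drug, not the operation. In the other arm, Section 5.2.1 states: "Subjects in Group A will have complete surgical resection of all detectable melanoma following Course 1 of hu14.18-IL2".

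Table 7A footnote 1 (Section 7.4.2) says that research samples scheduled for baseline "can be obtained at any time from 3weeks prior to randomization until just prior to (within 10 minutes) beginning study treatment". No rule ties the draw to the date of surgery.

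Sampling differs by assay:
- **NK/ADCC** (Section 7.3.4, Table 7A footnote 5): one baseline, then samples in Courses 2 and 3 only, on selected patients.
- **T-cell studies** (Section 7.3.6, Table 7A footnote 6): one baseline, then the ends of Courses 2 and 3, also on selected subjects.
- **Soluble IL2 receptor and anti-hu14.18-IL2 antibody** (Table 7A; Section 7.3.1 for the antibody): a baseline plus a Course 1 day 1 pre-infusion sample.

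Section 9.4.5 says that within each group "differences between pre-IC treatment values and post-IC treatment values will be evaluated by paired t-tests and/or non-parametric Wilcoxon test". The parameters it lists include NK/ADCC but not T-cell reactivity, which is to be analysed descriptively. It does not say which sample is the pre-IC value for each assay.

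**The concern.** Objectives 2.2.2 and 2.2.6 ask what the drug does to the immune system. For NK/ADCC and T cells, Group A cannot separate the drug from surgery: its operation falls between Courses 1 and 2, and all its later samples come from Courses 2 and 3. Group B is the only arm whose within-subject change in these assays can exclude the operation, and then only if its baseline is post-operative. Footnote 1 leaves that to scheduling, subject by subject.

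A pre-operative baseline puts a resection, possibly a thoracotomy or laparotomy, and the removal of all visible tumour into a change labelled pre-IC to post-IC. Section 1.5.4.4 expects any later Phase III trial to use Group B's schedule, so this is the contrast a reader would carry forward. The plan already recognises the same attribution problem for toxicity: Section 5.4.1 leaves the period from surgery to recovery out of DLT evaluation. The immunology has no matching rule.

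**Working it through.** **1. The plan's own figure.** Section 9.3.2 gives 80% power for 1.5 SD and 63% for 1.25 SD, for a two-sample t-test with 8 per arm at two-sided 0.05. With noncentral t, df = 14 and noncentrality d × √(8/2):
- d = 1.5: noncentrality 3.0, power 79.7%.
- d = 1.25: noncentrality 2.5, power 64.3%.

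Both agree with the plan to within 2 points, so the same framework is used below.

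**2. The window in Group B.** Three weeks before randomization plus 2 to 4 weeks of recovery is 21 + 14 = 35 to 21 + 28 = 49 days. Table 6B footnote 3 sets the outer limit on recovery ("If 8 weeks pass post-operatively, and the treating physician(s) still feel(s) that the subject is not fit to continue"), giving up to 21 + 56 = 77 days. Any interval from randomization to surgery is extra. The operation lies inside the window. In Group A the whole window is pre-operative.

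**3. Paired test in Group B with no drug effect.** Assumptions, none given in the documents: surgery shifts the assay by s = 0.5 to 1.0 SD, the shift is in place by a post-operative baseline and lasts into Courses 2 and 3, and the within-subject correlation ρ is 0.5 to 0.7.

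SD of change = √(2(1 − ρ)), which is 1.0 at ρ = 0.5 and √0.6 = 0.775 at ρ = 0.7. Standardised shift e = s / SD of change. If all 8 baselines are pre-operative, the rejection rate is noncentral t with df = 7 and noncentrality e√8. The half-and-half case was simulated (200,000 trials).

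| s | ρ | e | e√8 | all 8 pre-operative | 4 of 8 pre-operative | none |
|---|---|---|---|---|---|---|
| 0.5 | 0.5 | 0.50 | 1.41 | 23% | 8.5% | 5% |
| 0.5 | 0.7 | 0.65 | 1.83 | 35% | 10.5% | 5% |
| 1.0 | 0.5 | 1.00 | 2.83 | 68% | 17% | 5% |
| 1.0 | 0.7 | 1.29 | 3.65 | 88% | 22% | 5% |

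NK/ADCC is done on selected patients, so n may be below 8. With n = 4 (df = 3, noncentrality e√4 = 1.00 to 2.58) the all-pre-operative rate is 11% to 43%. The bias in the mean change is the same; the test is only less able to show it.

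**4. Between-arm test on change to Courses 2-3.** Group A's change always contains the shift. Under the same assumptions, with 8 per arm:
- All Group B baselines pre-operative: 5%, because both arms span surgery.
- Half pre-operative: 7% to 17% (simulated).
- All post-operative: 15% to 67% (df = 14, noncentrality e × √(8/2) = 1.00 to 2.58).

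**5. Which assays are affected.** The serum assays have a Course 1 day 1 pre-infusion sample, which is post-operative in Group B. If that sample is the pre-IC value, their paired contrast does not span surgery. T-cell reactivity has no planned test, so the rates in step 3 apply to NK/ADCC only; for T cells the issue is the meaning of the described change.

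**The case against.** The strongest reply is that a pre-operative Group B baseline matches Group A's, with tumour in place in both, and that moving it makes the arms less alike. Step 4 confirms this for comparisons of change, and that part stands. But both arms receive the same drug and differ only in the order of surgery and Course 1, so the between-arm contrast of change for these assays does not measure the drug effect under either timing. The within-arm contrast in Group B can.

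Two stronger readings are tempting and should not be made.
- *Footnote 1 is what spoils the between-arm comparison.* The documents do not support this. Group A's change spans surgery by design, and Section 9.4.5 does not say whether the two-sample test uses change or level.
- *Section 9.4.2 feeds pre-operative values into the paired tests.* Its sentence, "If the pre-treatment value is missing, the measurement recorded at the screening visit will be substituted", stands under Baseline Comparability. Section 9.4.5 has its own provision for missing data (regression-type imputation) and does not repeat the rule. Table 7A also has no separate screening draw for NK/ADCC or T cells. At most this is an ambiguity to close.

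It is also fair that these are secondary, exploratory tests without multiplicity adjustment, in a pilot of 16 subjects. That limits the consequence but does not make the baseline interpretable.

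**Conclusion.** The point holds for NK/ADCC and T-cell assays within Group B. As written, the plan allows their only pre-treatment sample to fall on either side of the operation, differently from subject to subject. The paired NK/ADCC test can then be falsely positive in 23% to 88% of trials (all baselines pre-operative) or about 8.5% to 22% (half), against 5% when all are post-operative. These figures rest on an assumed lasting surgical shift of 0.5 to 1.0 SD, correlation 0.5 to 0.7 and n = 8. A smaller or transient shift would do less harm.

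A reader might infer that all the immunology is compromised. It is not: soluble IL2 receptor and antibody are unaffected if the day 1 pre-infusion sample is used. The primary endpoints are untouched. This is a cheap improvement to secondary analyses.

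**What to change.** 1. Amend Table 7A footnote 1: in Group B, draw the NK/ADCC and T-cell baseline after recovery from surgery and before the first infusion, on Course 1 day 1 or within the 7 days before it.
2. In Section 9.4.5, name the Course 1 day 1 pre-infusion sample as the pre-IC value for soluble IL2 receptor and antibody, and state that a pre-operative screening value is not used as the Group B pre-IC value in these tests.
3. Record the date of each draw relative to surgery.
4. State that Group A's NK/ADCC and T-cell changes to Courses 2-3 always span surgery, so between-arm comparisons of change in these assays are descriptive and do not isolate the drug.
5. Reconcile the arm labels: Section 9 calls the surgery-first arm Group A.

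Cost: one footnote and a few sentences in Section 9. The tubes and volumes are unchanged, so the Section 7.7 blood totals do not rise, and a pre-infusion research draw already takes place on Course 1 day 1. The downsides are less scheduling freedom and, in Group B, the loss of a tumour-in-place baseline matching Group A's. Keeping both samples would need an extra draw, to be checked against the Section 7.7 limit.

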7.5 Surgical pathology guidelines

7.5.1 Review of outside diagnostic material

Prior to surgery at the University of Wisconsin, slides of patients' prior diagnostic material will be reviewed by a pathologist to ensure accuracy of diagnoses and presence of melanoma at the resection site, as appropriate. As many of the biopsies demonstrating recurrence will likely be small needle cores or fine needle aspirates, extensive analysis of any inflammatory infiltrate prior to enrollment is unlikely to be possible in most cases. As described above, in a subset of patients from Groups A that have accessible lesions, we will attempt to obtain two core biopsies of these sites to later be fully resected: one biopsy prior to initiation of study treatment, and the second biopsy within one week (i.e., approximately days 5-7) of initiating study treatment. These biopsies will be bisected, with half submitted for paraffin sections and half frozen in OCT embedding media for sections (to be assessed as described in Sections 7.4.2 and 7.4.3).

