7.8 Analyses to be performed in laboratory correlate studies

In addition to the clinical outcome data from this study, and in addition to the laboratory studies planned for each patient based on analyses of required blood and tissue samples, we also plan to perform two elective laboratory correlate studies using blood and tissue from selected subjects. (These subjects will give informed consent to participate in these studies in addition to the main clinical study.) One of these laboratory correlate studies will enable us to obtain an elective biopsy prior to receiving treatment with the experimental agent(s) for subjects randomized to Group A that have subcutaneous lesions which are

readily accessible to punch or excisional biopsy. These biopsy specimens would come only from readily accessible lesions in a manner similar to that described previously so as not to put these subjects at additional undue risk. No subjects in Group B will be entered into this elective biopsy study since all of their clinically detectable disease will be resected prior to administration of hu14.18-IL2. From these pre-treatment research biopsy samples, we will evaluate the general histological appearance, and presence of any immune-cell infiltrate within the tumors before study treatment. More importantly, these elective pretreatment biopsies will enable us to use these for comparison purposes, when we evaluate the resected tumor obtained after the first course of treatment for subjects in Group A.

The other laboratory correlate study will obtain blood and tissue samples from subjects who have recurrence of their disease. These research samples will be subjected to the following analyses: the influence of the prior treatment on the immune system, the subjects' immune response against the agents *per se*, and histological studies similar to those described for the preceding correlate study, in order to evaluate potential changes in tumor biology that may be associated with recurrent disease.

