9.3.2 Sample Size/Accrual Rate

The first primary objective of this study is to evaluate the histological evidence of anti-tumor activity of hu14.18-IL2 by comparing pathological endpoints between the two groups after dichotomizing the evaluation of apoptosis, necrosis and cellular infiltrate into *positive* (i.e., the microscopic evaluation is classified as “low”, “medium”, or “high”) or *negative* (i.e., the evaluation is classified as “none”) using Fisher’s exact test. With eight subjects per group, a difference of 70% in the proportions of subjects classified as *positive* for necrosis, apoptosis, or cellular infiltrate between the two study arms will be detected with at least 82% power at a two-sided significance level of 0.1. A difference of 60% will be detected with at least 64%. Smaller differences are unlikely to be detected as statistically significant. The sample size chosen is sufficient to provide accuracy in the estimated rate of subjects classified as *positive*. Specifically, with eight subjects per group, the standard error of the proportions of subjects classified as *positive* necrosis, apoptosis, or cellular infiltrate for each group will be at most 0.18.

The second primary objective of this study is to evaluate the time to recurrence (duration of remission) and overall survival relative to historical control data described in Section 1.3.3. This study is not designed to detect differences in time to recurrence or overall survival between the two study arms. Instead, time to recurrence and overall survival time of both arms combined will be compared to historical controls qualitatively. Time to recurrence and overall survival time will be summarized using point estimates of the median time to recurrence/overall survival time and associated 90% confidence intervals. Furthermore, the two-year recurrence free survival rate and the two-year survival rate will be reported along with the corresponding 90% confidence intervals. The following table gives (two-sided) Wilson’s score 90% confidence intervals for the two-year survival/two-year recurrent-free survival rates, assuming a total sample size of 16 subjects.

Table 9: Ninety percent confidence bounds for two-year survival/two-year recurrent-free survival rates

Observed number of subjects alive/recurrent-free after 24 months	Proportions of subjects alive/recurrent-free after 24 months	Lower 90% confidence limit	Upper 90% confidence limit
2	0.12	0.04	0.32
4	0.25	0.12	0.45

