9.4.4 Primary Endpoints

Pathology evaluations of necrosis, apoptosis, and cellular infiltrate will be summarized in frequency tables (for each study arm). The proportions of subjects with tumor tissues classified as *positive* (i.e., the microscopic evaluation is classified as “low”, “medium”, or “high”) will be reported along with the corresponding 90% confidence intervals. The comparisons of pathology evaluations between the two study arms will be performed by Fisher’s exact test. For subjects in treatment group B, tumor tissues from biopsies obtained at study entry (pre-study biopsies) will be compared to surgically resected tumor tissues obtained after the first course of IC treatment. Paired comparisons of necrosis, apoptosis, and cellular infiltrate pathology evaluations will be performed using McNemar’s test.

Time to recurrence and overall survival will be summarized using point estimates of the median time to recurrence/overall survival and associated 90% confidence intervals. The data will be presented graphically using Kaplan-Meier plots. The two-year recurrence free survival rate and two-year survival rate will be reported along with the corresponding 90% confidence interval. Time to recurrence and overall survival will be contrasted to historical controls (47,49-53) as well as data from comparable subject groups being observed following surgically induced CR that may be published now and when the data from the present study are being analyzed.

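### On-study biopsies occur only in Group A, at sites later resected and scored for the primary histology comparison, and no rule keeps biopsy-site tissue out of the score

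*Combined protocol and SAP*

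**What the plan says.** Arm labels here follow the Schema and Section 5.2: Group A is treated before surgery and Group B is operated on first. Section 9 uses the labels the other way round.

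- **Who is biopsied.** Section 7.3.2, Table 7A (footnote 8) and Section 7.5.1 offer extra biopsies to consenting Group A subjects with accessible lesions. Section 7.8 adds: "No subjects in Group B will be entered into this elective biopsy study".
- **Where and when.** Section 7.5.1 describes "two core biopsies of these sites to later be fully resected", the first before treatment. The second falls on about days 3-5 (7.3.2), 4-7 (Table 7A, footnote 8) or 5-7 (7.5.1). Section 7.3.2 specifies a 3 or 6 mm punch.
- **Resection.** Section 5.2.1: "Surgical resection will be scheduled for 7-14 days following the completion of the first 3-day course of therapy (i.e., days 10-17").
- **Scoring.** Section 7.5.4 grades necrosis, apoptosis and cellular infiltrate on the resected melanoma. Section 9.3.2 counts low, medium or high as positive and only none as negative.
- **Test.** Section 9.4.4: "comparisons of pathology evaluations between the two study arms will be performed by" Fisher's exact test. Section 9.3.2 sets eight subjects per group and a two-sided level of 0.1.

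No section excludes a biopsied nodule or tract from scoring, says which lesion represents a subject with several, or plans an analysis by biopsy status.

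**The concern.** Section 1.5.4.3 justifies Group B as a control whose tumors are handled identically to Group A's, so that a histological difference reflects one course of drug. A procedure on the tumor in one arm only, shortly before resection, breaks that symmetry. Any necrosis or inflammation it leaves is confounded with treatment. Under none-versus-any scoring a small focus is enough, and Section 7.5.3 already expects infiltrates to be patchy. A blinded reader does not help, because the difference is in the tissue. The paired comparison in Section 9.4.4 is exposed too: resected tissue may carry on-study biopsy injury that the pre-study biopsy cannot.

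**Working it through.** **1. The planned test.** Section 9.3.2 says of a 70-point difference that it "will be detected with at least 82% power at a two-sided significance level of 0.1", and of 60 points: "A difference of 60% will be detected with at least 64"%. It gives no background rate. Enumerating Fisher's exact test with 8 per arm gives 81.2% for 10% vs 80% and 65.7% for 10% vs 70%. The minima over all background rates are 80.0% and 61.4%. A normal approximation with continuity correction, n' = (8 - 1/0.7)²/8 = 5.40, gives a minimum of 82.05% for the 70-point difference (at 15% vs 85%). The stated figures are therefore close to reproduced, and the same test is used below.

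**2. Gap between biopsy and resection.** The shortest gap is day 10 - day 7 = 3 days. The longest is day 17 - day 3 = 14 days.

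**3. Model with no drug effect.** Let k be the number of the 8 Group A subjects biopsied, q the chance that biopsy turns an otherwise negative specimen positive, and p0 the background positive rate. **None of the three is in the documents; all are assumptions.**

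- Positives in A: Bin(k, p0 + (1 - p0)q) + Bin(8 - k, p0)
- Positives in B: Bin(8, p0)
- False difference in proportions: (k/8)(1 - p0)q

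For example, k = 4, q = 0.5, p0 = 0.2 gives (4/8)(0.8)(0.5) = 20 points. With q = 1 it is 40 points.

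**4. Probability that the planned test rejects** (exact enumeration; nominal level 10%):

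| k | q | p0 = 10% | 20% | 30% | 50% |
|---|---|---|---|---|---|
| 0 | – | 0.4% | 2.0% | 2.8% | 2.6% |
| 2 | 1 | 5.0% | 6.4% | 5.1% | 3.6% |
| 3 | 1 | 18% | 13% | 9% | 6% |
| 4 | 0.5 | 9.5% | 8.0% | 6.0% | 4.1% |
| 4 | 1 | 45% | 24% | 15% | 9% |
| 6 | 0.5 | 24% | 16% | 11% | 7% |

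For k = 2 the maximum over every p0 and q is 6.5%. For k = 4 and q = 0.5 the maximum over p0 is 9.5%.

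**5. Sensitivity to a few specimens.** With 0 of 8 positive in Group B, 4 of 8 in Group A is already significant (p = 0.077).

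**The case against.** The strongest reply is that this shows a possible bias and not a failed test. Fisher's test is very conservative at this size, so a moderate artefact is absorbed: the middle case (k = 4, q = 0.5) stays under 10% at every background rate. Higher background rates shrink the effect, and a low rate for infiltrate cannot be taken for granted. All of that stands.

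The overlap between biopsied and scored tissue is also partial. The biopsies are optional and limited to a subset. Nodules too large for the punch may be excised instead (7.3.2). Up to three sites may be resected (3.1.1.1). Objective 2.2.5 asks for resected tumor from the same subject, not the same lesion. In addition, Sections 1.5.4.2 and 1.5.4.3 require a pre-study biopsy in both arms, and Group B is resected on study entry, so some Group B specimens may carry recent biopsy change. This counterweight is partial, because Section 3.1.11 accepts earlier tissue and nothing in Group B matches biopsies taken during the first course.

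The continuous 0-100% necrosis measure in Section 7.5.4 would be little moved by a small focus, but the primary test uses the dichotomy.

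A reader might infer that biopsy injury will produce a false drug effect, or that the comparison is invalid. The documents do not support either. They contain no data on what a biopsy does to these scores, so the direction is plausible but assumed.

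**Conclusion.** The concern holds as an uncontrolled source of bias of unknown size. The one-arm biopsies, the later resection of the same sites, the scoring of that tissue and the lack of any safeguard are all in the text. The false difference is (k/8)(1 - p0)q, but k, q and p0 are assumptions. The false-positive rate stays below the nominal 10% with two subjects biopsied. It passes 10% only when a larger share of the arm is biopsied and conversion is substantial: three subjects need nearly all specimens converted, and four need more than half at a low background rate. Even where the test holds its level, the estimated difference between arms would be shifted. In a 16-subject pilot this justifies an inexpensive safeguard set before slides are read, and no change of design.

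**What to change.** - **Section 7.5.4:** for each resected lesion, record whether and when it was biopsied, separately for diagnostic and on-study biopsies. In **both arms**, score necrosis, apoptosis and infiltrate on tumor away from any identifiable biopsy site or tract. Do not prefer unbiopsied nodules in Group A only: that would remove accessible lesions from one arm and create a new selection difference.
- **Section 9.4.4:** keep all subjects in the primary comparison. Add a sensitivity analysis excluding subjects whose only scorable lesion was biopsied on study, and label it as non-randomised, since exclusion depends on accessibility and consent.
- **Consistency:** reconcile the three windows for the second biopsy and the reversed Group A/B labels in Section 9.

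**Cost:** a pathology instruction, one data field per lesion and one extra analysis, with no new procedure. Slightly less tissue is scorable. Power of the sensitivity analysis at 10% vs 80% is 81.2% with none dropped from Group A, 81.7% with two, 80.7% with four and 52.0% with six (not monotone because the test is discrete). It would therefore be weak if most of Group A were excluded.
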